4. Assessment of the rectoanal inhibitory reflex (RAIR)- a balloon distension test will be performed. The rectal balloon attached to the pressure probe will be gradually filled with air starting at 30ccs and in 10cc increments until a RAIR reflex is identified. Balloon distension increases pressure registered by intrarectal sensors. The volume of air injected is displayed along with the pressure change it induced. Balloon distension normally produces a graded relaxation of the anal canal musculature. The RAIR reflex should appear as a relaxation of the IAS which starts on the rectal side of the anal canal which spreads caudally.

Manometric Parameters

RESTING	SQUEEZE
Maximum sphincter pressure	Maximum sphincter pressure

Mean sphincter pressure Length of IAS and EAS Length of anal verge to centre of anal canal BEAR DOWN Residual anal pressure Percentage anal relaxation Intrarectal pressure Rectoanal pressure differential	Duration of sustained squeeze BALLOON INFLATION (cc) Presence of rectoanal inhibitory reflex (RAIR) First sensation Urge to defecate Discomfort Minimum rectal compliance Maximum rectal compliance
---	--

The 10 Question Bowel Survey, SCI Bowel Management QOL, SCI Bladder Complication, SCI Bladder Management, and Wexner’s Incontinence Scale will be administered. A subgroup of 20 subjects who report either constipation or FI and who have an incomplete injury as defined by the ASIA Impairment Scale will be identified, and will have the option of enrolling in part 2 of the study; standard bowel biofeedback training.

[figure not shown]
Part 2: Biofeedback Training:

Once a subject has been identified as a candidate for biofeedback based on the ASIA examination (SCI incomplete ASIA B, C, D) and expressed interest in participation, an informed consent interview will be scheduled. Once written consent is obtained, a training schedule of twice weekly sessions will be scheduled. Twenty subjects will be recruited for this arm of the study. Each training session will last for approximately 60 minutes.

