The VA cares for approximately 40,000 veterans with SCI. In addition there are over 200,000 non-veterans with SCI in the US. Many of these individuals have neurogenic bowel and suffer from the embarrassment and social isolation caused by FI. The life expectancy of SCI patients has dramatically increased, with most SCI patients living up to 60 years of age (10 years less than non SCI patients). Given that the average age of injury is 37 years and that 25% of SCI patients are between 19 to 25 years, these individuals have to live with the ignominy of fecal incontinence for many years to come. The current practice of using multifaceted programs for bowel care leaves much to be desired, as many SCI patients still suffer from FI and constipation. In this respect it has become urgent to develop other treatment options for neurogenic bowel complications in order to improve quality of life and to preempt further GI complications/

Relevance of the proposed work to the VA patient care mission

The VA system cares for a large number of persons with SCI, and FI and time consuming and cumbersome bowel care has been identified as a major QOL issue among the veterans. Despite extensive efforts to understand its pathophysiology and numerous clinical guidelines for its management, FI and constipation remain tenacious problems that limit the social interactions of veterans with SCI. The proposed work will result in the only known data regarding the efficacy of bowel biofeedback treatment and the outcome of FI in person with SCI. Furthermore, to the extent that biofeedback treatment can improve FI, this research should be cost effective because it would prevent physical and psychological comorbidities associated with neurogenic bowel as it is far less expensive to provide bio feedback treatment than to treat chronic conditions like depression arising from social isolation, and dermatological treatments arising from exposure of the skin to FI. Providing veterans with cutting edge preventive care is a key component of the VA patient care mission.

F. LIST OF KEY BIBLIOGRAPHICAL REFERENCES

1. Devivo, M.J., *Epidemiology of traumatic spinal cord injury: trends and future implications*. Spinal Cord. **50**(5): p. 365-72.
2. Valles, M., et al., *Bowel dysfunction in patients with motor complete spinal cord injury: clinical, neurological, and pathophysiological associations*. Am J Gastroenterol, 2006. **101**(10): p. 2290-9.

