Utility of an Animated Bowel Biofeedback Training Routine to Improve Bowel Function in Individuals With SCI

NCT02406859

March 10, 2013

Statistical Analysis Plan

For the continuous dependent, independent and demographic variables, descriptive statistics will be performed and expressed as group mean ± SD, with 95% confidence intervals and ranges. To examine the effect of the training on manometric and subjective parameters (groups: stratified by level of injury and completeness) analysis of variance (ANOVA) with repeated measures on visit (Pre, Post) will be performed. In the event of non-normal distribution of study outcomes, non-parametric ranking statistics will be applied as appropriate. An a priori level of significance will be set at P≤0.05. IBM SPSS Statistics version 22 will be used for all analyses.

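### No outcome is named to carry the efficacy claim, so the SAP's 0.05 threshold is not the error rate of the study's conclusion about training

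*SAP*

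**What the plan says.** The SAP is a single paragraph. Its stated purpose for the inferential analysis is "To examine the effect of the training on manometric and subjective parameters", with groups defined by level and completeness of injury. The method is "analysis of variance (ANOVA) with repeated measures on visit (Pre, Post) will be performed", with rank-based methods if the data are not normal. The only decision rule is "An a priori level of significance will be set at P≤0.05".

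The protocol supplies the outcomes in two places.

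- **Section A, Aim 2a-c** gives the training outcomes: rectal and sphincter pressures during squeeze and bear-down, sensitivity and strength of the RAIR, and incontinence and constipation by the bowel surveys and Wexner's scale.
- **Section C, Part 1 (Manometric Parameters)** gives a longer list. Beside a maximum sphincter pressure at rest and at squeeze, it has "Mean sphincter pressure Length of IAS and EAS Length of anal verge to centre of anal canal" at rest, "Duration of sustained squeeze" for squeeze, "Residual anal pressure Percentage anal relaxation Intrarectal pressure Rectoanal pressure differential" for bear-down and "Presence of rectoanal inhibitory reflex (RAIR) First sensation Urge to defecate Discomfort Minimum rectal compliance Maximum rectal compliance" for balloon inflation. Five surveys are also administered.

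Section C, Part 2 repeats manometry and surveys after 6 weeks of in-house training and again after 6 weeks of home exercise. Twenty subjects are to be trained.

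Neither document names a primary outcome, orders the outcomes, adjusts for multiple testing or restricts any test to exploratory use. Section B calls the study a pilot. Aim 2 nevertheless includes assessing efficacy, and Section E says "The proposed work will result in the only known data regarding the efficacy of bowel biofeedback treatment".

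**The concern.** A 5% significance level describes the false-positive risk of one test fixed in advance. Here the test that decides whether training works has not been fixed. A reader of the results could not tell whether a significant squeeze pressure, sensation threshold or survey score was the result the study was designed to produce or the one of many that happened to cross the line.

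The visit is also open: the protocol has two post-training assessments, while the SAP speaks only of Pre and Post. Each ANOVA with injury groups adds a group-by-visit test, which could also be read as a training effect in a subgroup.

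At stake is the strength of any efficacy statement from what the protocol expects to be the only data on this question in people with SCI.

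**Working it through.** The plan gives no power, effect size, SD or overall error rate, so there is no figure of its own to reproduce. The check asks how often at least one visit effect reaches P≤0.05 when training changes nothing.

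**Inputs**

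- Level per test: 0.05 (SAP).
- Subjects: 20 (protocol, Section C, Part 2).
- Correlation between outcomes: not given, so it is an assumption and is varied.
- Outcome count: the SAP does not state it, so a range is used.

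**Counting the outcomes**

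- *Narrow reading, Aim 2a-c.* Rectal and sphincter pressure in each of two maneuvers is 4; RAIR sensitivity and strength is 2; the 10-item survey and Wexner's scale are 2. Total 4 + 2 + 2 = 8. With one pressure per maneuver it is 2 + 2 + 2 = 6.
- *Wide reading, Section C.* Resting 4 + squeeze 2 + bear-down 4 + balloon 6 = 16 manometric parameters. Adding five surveys gives 21. Leaving out the three SCI-QOL surveys, whose stated purpose is to test those instruments, gives 18.

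**Independent outcomes:** P(at least one) = 1 − 0.95^k; expected number = 0.05k.

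| Outcomes k | P(at least one) | Expected false positives |
|---|---|---|
| 6 | 1 − 0.95^6 = 26% | 0.30 |
| 8 | 1 − 0.95^8 = 34% | 0.40 |
| 18 | 1 − 0.95^18 = 60% | 0.90 |
| 21 | 1 − 0.95^21 = 66% | 1.05 |

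**Correlated outcomes:** null simulation of 20 subjects with normal change scores sharing a common correlation, each tested by a two-sided paired t-test at 0.05.

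| Common correlation | 8 outcomes | 21 outcomes |
|---|---|---|
| 0.5 | about 26% | about 44% |
| 0.7 | about 20% | about 31% |
| 0.9 | about 12 to 13% | about 16% |

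Modelling two injury groups of 10 (an assumed split) hardly changes the 21-outcome figures: 45%, 32% and 17%. If outcomes correlate only within families (rest, squeeze, bear-down, balloon, surveys), the 21-outcome figures are 58% at 0.5, 52% at 0.7 and 40% at 0.9.

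**Adding the group-by-visit test:** 21 × 2 = 42 tests. If independent, 1 − 0.95^42 = 88%. At common correlation 0.5, with two groups of 10, it is about 68%.

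**One named primary outcome at one visit:** 5%.

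**The case against.** The strongest reply is that this is a pilot, and Section B says so. Its aims include describing anorectal pressure profiles and identifying responders. Adjusting every test in such a study is not standard, and Section E promises data rather than a confirmatory result. It stands that across-the-board adjustment is not required. But Aim 2 includes efficacy, with directional hypotheses, and no text limits the tests to hypothesis generation. The pilot label does not say which result may support a claim.

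Three stronger readings are tempting, and the documents do not support them.

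- *A reader might infer that all 21 listed outcomes will be tested for efficacy.* The SAP does not say every parameter, the Section C list may be only a recording list, three surveys have a different stated purpose, and presence of the RAIR is binary and does not suit ANOVA. Aim 2a-c supports about 6 to 8. Twenty-one is close to the top of the range, not the plan's stated number.
- *A reader might infer that a false-positive training effect is more likely than not.* That holds for 18 to 21 independent or weakly correlated outcomes. It fails on the narrow count, and for 21 outcomes at a common correlation of 0.5 or more. Several parameters come from the same recording, so full independence is implausible.
- *A reader might count three ANOVA effects per outcome, 63 tests, and quote 1 − 0.95^63 = 96%.* Group main effects average over visits and cannot show a training effect. Section B also expects function to differ by injury, so they are not null.

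The figures count effects in either direction. Counting only favourable ones, 21 independent tests give 1 − 0.975^21 = 41%, and 8 give 1 − 0.975^8 = 18%, against 2.5% for one test. The SAP does not fix a favourable direction for each parameter.

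**Conclusion.** The point holds: the SAP's 0.05 is not the error rate of an efficacy conclusion drawn from this plan. On the count most favourable to the plan, 6 to 8 outcomes, the error is 26 to 34% under independence. For 8 outcomes it remains about 12 to 13%, more than twice nominal, even at correlation 0.9. On the wide count it is 60 to 66% under independence and, for 21 outcomes, about 16% at correlation 0.9. Group-by-visit tests raise it further.

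The size rests on two unknowns, the count and the correlation. The direction does not depend on either, short of outcomes so highly correlated that they are in effect one. This is a matter the plan should settle before analysis; it does not undermine the data collection or the descriptive aims.

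**What to change.** Before analysis, name in the SAP one primary outcome at one stated visit for all 20 trained subjects and test it at 0.05. The sponsor should choose it from the Aim 2 outcomes, for example a bowel symptom score from Aim 2c. The instrument needs naming exactly, since the constipation hypothesis in Section A cites a Bowel and Bladder Survey while Section C uses the 10-item survey.

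Report all other outcomes, the other post-training visit, and the group and group-by-visit terms as exploratory, with estimates and 95% confidence intervals, and draw no efficacy claim from them. If no outcome is named, state that all tests are exploratory and that no efficacy conclusion will be drawn.

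If the sponsor prefers one outcome per symptom type, control the overall 0.05 across the two (for example with Holm), state how subjects with both symptoms are handled, and accept the loss of power. Assuming 10 subjects per type (the documents give no split), 80% power on a paired t-test at 0.025 needs a mean change of about 1.14 SD, against 0.66 SD for 20 subjects at 0.05.

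The single-outcome version costs SAP wording only. Its downside is that fewer results can be called significant.
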